4.4.3 Exploratory Endpoints

Exploratory endpoints will be driven by a fundamental analysis of mean changes in clinician rating scales and patient QoL and PRO instruments compared from baseline to one or more visit timepoints. Mean changes in epigenetic markers also will be assessed. In addition, data captured by the health tracking wearable device will be assessed. For all exploratory endpoints, appropriate statistical methods will be employed as described, more generally in Section 13.5. A formal outline of the statistical methods to be employed will be detailed in the SAP.

- At Screening, participants will confirm that they have had a traumatic event, captured in the LEC-5 and that they have a minimum score of at least 33 as determined the PCL-5, respectively.
- Mean changes from baseline to various study visit timepoints (e.g., Study Day 7) will be calculated for the following instruments:
 - General Anxiety Disorder 7 Item Scale (GAD-7)
 - Patient Health Questionnaire-9 (PHQ -9)
 - Healing Experience of All Life Stressors (NIH HEALS)
 - Brief Pain Inventory (BPI)
 - Columbia-Suicide Severity Rating Scale (C-SSRS)

CONFIDENTIAL

- Profile of Mood States (POMS)
- Sheehan Disability Scale (SDS)
- Watts Connectedness Scale (WCS)
- Mystical Experience Questionnaire-revised (MEQ30)
- Challenging Experience Questionnaire (CEQ)
- 5-Dimensional Altered States of Consciousness Rating Scale (5D-ASC)
- Alcohol Use Disorders Identification Test (AUDIT)
- Drug Use Disorders Identification Test (DUDIT)
- Mean changes in epigenetic markers from baseline to various timepoints will be calculated for psychiatric and cardiovascular genes.
- Data collected by a health tracking wearable device such as nightly sleep duration, sleep latency, sleep efficiency, heart rate and heart rate variability during sleep, and daily steps will be calculated.

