7.1.3 Screening Period (Day -30 to -1)

If after the pre-screening telephone interview, the study site staff and/or the investigator feel the candidate may be suitable for the study, a Screening visit will be scheduled.

The initial Screening Visit will include the following protocol mandated activities, tests, examinations, assessments and procedures:

- Explain and obtain written informed consent from the candidate prior to performing any study-specific tests or evaluations.
- Issue a 3-digit screening number and record the appropriate information on the Screening Log.
- Review the participant's medical and psychological history including current and past medications and therapies.
 - Have the participant sign a medical release form to allow the Investigator to review his/her medical records to ensure the participant has no underlying medical conditions that would preclude their participation in the trial and confirm the PTSD diagnosis.
- Review the LEC and PCL-5 checklists.
- Review with female participants of childbearing potential their ability to become pregnant and commitment to practice appropriate birth control as defined in this protocol for the total duration of the study.
- The following clinician rating scales and participant QoL and PRO instruments should be administered and/or completed by the participant, respectively:
 - LEC-5 (at least one traumatic event causative for a diagnosis of PTSD)
 - PCL-5 (a score of at least 33)
 - GAD-7 (scores of ≥ 15 will exclude the participant)
 - PHQ-9 (scores of ≥ 20 will exclude the participant)
 - NIH HEALS
 - BPI
 - C-SSRS (category ratings of 4 or 5 will exclude the participant)
 - SDS
 - AUDIT
 - DUDIT
- Collect vital signs (blood pressure, pulse, body temperature, respiratory rate and pulse oximetry).
 - Perform a medical history directed physical examination. The examination will involve the following procedures:
 - Height/weight.
 - Examination of head, eyes, ears, nose, throat, skin, heart, lungs, abdomen and extremities.

CONFIDENTIAL

- Brief neurological exam (cranial nerves 2-12, sensory, motor, reflexes and cerebellar function).
- Obtain 12 lead ECG
- Collect urine for the following laboratory analyses:
 - Urine pregnancy test in women of childbearing potential.
 - Qualitative rapid urine drug screen.
 - Qualitative urine ethyl glucuronide (EtG) test to assess alcohol consumption.
- Collect a blood sample for clinical laboratory evaluations.

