Study Medication Administration

Provided the participant remains eligible, they will undergo a symbolic ceremony in which intentions are set and then be instructed to self-administer the study drug.

- The participant will self-administer, under observation, a whole, dried, ground organic psilocybin mushroom (RTT1121 also called JMF-01) which has been milled and formulated into 3 solid chocolates.
 - A physician will be onsite, or if observing via video conferencing can reach the study site within 10 minutes in case of a medical emergency.

Post-Dose Monitoring and Assessments

Following the self-administration of the single dose of study drug, participants will be instructed to lie down wearing eyeshades and listen to a preselected music playlist via headphones and speakers. Participants will be closely monitored for medical and psychological (including psychosis) adverse effects to ensure their safety and well-being. Participants also will be assessed via clinician rating scales.

In addition to the therapists (and group) support provided, a trained therapy dog also will be available in the dosing room to offer additional support, if requested by the participant.

- Vital signs are to be measured every 30 minutes for at least 8 hours following study drug administration.
 - If vital signs are abnormal at 8 hours, the participant will remain at the study site for continued observation until the measurements return to baseline values, or the Investigator deems that not further monitoring is needed. Vital sign measurements listed below may be considered abnormal; (however, the Investigator may override these values):
 - Blood pressure above 140/90 mmHg
 - Heart rate outside the range of 50-90 beats per minute
 - Respiratory rate
 - Pulse oximetry – SpO2 ratio $< 92\%$
- Blood samples for PK profiling will be collected at the following timepoints
 - 30 minutes (± 2 mins)

CONFIDENTIAL

- 60 minutes (± 5 mins)
- 90 minutes (± 5 mins)
- 120 minutes / 2 hours (± 5 mins)
- 4 hours (± 15 minutes)
- 8 hours (± 15 minutes)
- Manage participant's complaints of pain and administer pain medication as warranted and record the type(s) and amount(s) administered.
- Nearing the 8-hour timepoint, the following clinician rating scales and participant QoL and PRO instruments should be administered and/or completed by the participant, respectively:
 - GAD-7
 - PHQ-9
 - C-SSRS
 - MEQ30-revised
 - CEQ
 - 5D-ACS
 - WCS
 - BPI

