8.5. Suicidal Ideation

The Columbia Suicide Severity Rating Scale (C-SSRS) is a clinician-administered measure of suicidal behavior devised to detect potential suicidal thoughts or behaviors during a clinical trial (Posner 2007). It consists of a "Baseline" form that assesses lifetime suicidal ideation, intensity, and behavior, and a form for assessing current suicidal ideation and intensity. The C-SSRS consists of a series of questions and can be administered via face-to-face interview or over the telephone. The C-SSRS is a detailed interview, but the full interview is needed only if the initial screening questions about suicidal ideation and behavior are positive. The screening questions should be completed for every participant and as needed if a participant is showing any signs of being suicidal. For management of suicidal thoughts, see Section 10.3 Risk Mitigation.

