12.5. Analyses of Exploratory Objectives

The following is an outline of the planned analyses to be done for various exploratory objectives (and associate endpoints).

- Analyses of changes from baseline for continuous questionnaires will be summarized descriptively by visit. and analyzed using repeated measures ANCOVA or generalized linear mixed modeling, as described in the SAP. The statistical significance of the change from baseline ($p < 0.05$) will be determined for each measure. 95% confidence intervals will also be derived.
- Change in average sleep duration, sleep latency, sleep efficiency, sleep timing, sleep consistency, nightly heart rate variability, and daily steps from baseline (through product use) will be assessed, as measured by the health tracking wearable device.

As heart rate and heart rate variability are highly confoundable metrics, analysis of these metrics will be done on all data collected but limited to days without unusual conditions reported by the participants (e.g., unusual alcohol consumption, changes in medication, very high activity, illness, death of a family member or other extraordinary stress unrelated to study participation).

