5. Please rate your pain by marking the box beside the number that best describes your pain on the **average**.

☐ 0 ☐ 1 ☐ 2 ☐ 3 ☐ 4 ☐ 5 ☐ 6 ☐ 7 ☐ 8 ☐ 9 ☐ 10
No Pain Pain As Bad As You Can Imagine

6. Please rate your pain by marking the box beside the number that tells how much pain you have **right now**.

☐ 0 ☐ 1 ☐ 2 ☐ 3 ☐ 4 ☐ 5 ☐ 6 ☐ 7 ☐ 8 ☐ 9 ☐ 10
No Pain Pain As Bad As You Can Imagine

Date:

--	--

 /

--	--

 /

--	--

(month) (day) (year)

Subject's Initials :

Study Subject #:

Study Name: _____

Protocol #:

Pl: _____

Revision: 07/01/05

PLEASE USE
BLACK INK PEN

7. What treatments or medications are you receiving for your pain?

8. In the last 24 hours, how much relief have pain treatments or medications provided? Please mark the box below the percentage that most shows how much relief you have received.

0% 10% 20% 30% 40% 50% 60% 70% 80% 90% 100%

☐ No Relief ☐ Complete Relief

9. Mark the box beside the number that describes how, during the past 24 hours, pain has interfered with your:

A. General Activity

☒ 0 Does Not Interfere
 ☐ 1
 ☐ 2
 ☐ 3
 ☐ 4
 ☐ 5
 ☐ 6
 ☐ 7
 ☐ 8
 ☐ 9
 ☐ 10 Completely Interferes

B. Mood

☐ 0 Does Not Interfere
 ☐ 1
 ☐ 2
 ☐ 3
 ☐ 4
 ☐ 5
 ☐ 6
 ☐ 7
 ☐ 8
 ☐ 9
 ☐ 10 Completely Interferes

C. Walking ability

☐ 0 ☐ 1 ☐ 2 ☐ 3 ☐ 4 ☐ 5 ☐ 6 ☐ 7 ☐ 8 ☐ 9 ☐ 10
Does Not Completely
Interfere Interferes

D. Normal Work (includes both work outside the home and housework)

☐ 0 ☐ 1 ☐ 2 ☐ 3 ☐ 4 ☐ 5 ☐ 6 ☐ 7 ☐ 8 ☐ 9 ☐ 10
Does Not Completely Interferes

E. Relations with other people

☐ 0 ☐ 1 ☐ 2 ☐ 3 ☐ 4 ☐ 5 ☐ 6 ☐ 7 ☐ 8 ☐ 9 ☐ 10
Does Not Completely
Interfere Interferes

F. Sleep

☒ 0 Does Not Interfere ☐ 1 ☐ 2 ☐ 3 ☐ 4 ☐ 5 ☐ 6 ☐ 7 ☐ 8 ☐ 9 ☐ 10 Completely Interferes

G. Enjoyment of life

[illegible]

Exhibit 7

Columbia-Suicide Severity Rating Scale (C-SSRS)

SUICIDAL IDEATION	

Ask questions 1 and 2. If both are negative, proceed to "Suicidal Behavior" section. If the answer to question 2 is "yes", ask questions 3, 4 and 5. If the answer to question 1 and/or 2 is "yes", complete "Intensity of Ideation" section below.
	Since Last Visit

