Fatigued					
Competent					
Annoyed					
Discouraged					
Resentful					
Nervous					
Miserable					
Confident					
Bitter					
Exhausted					
Anxious					
Helpless					
Weary					
Satisfied					
Bewildered					
Furious					
Full of Pep					
Worthless					
Forgetful					
Vigorous					
Uncertain about things					
Bushed					
Embarrassed					

Exhibit 9
Sheehan Disability Scale (SDS)

Sheehan Disability Scale

A brief, patient rated, measure of disability and impairment.
Please mark ONE circle for each scale.

WORK* / SCHOOL

The symptoms have disrupted your work / school work:

Not at all Mildly Moderately Markedly Extremely

0 ← 1 2 3 4 5 6 7 8 9 → 10

☐ I have not worked / studied at all during the past week for reasons unrelated to the disorder.
* Work includes paid, unpaid volunteer work or training

SOCIAL LIFE

The symptoms have disrupted your social life / leisure activities:

Not at all Mildly Moderately Markedly Extremely

0 ← 1 2 3 4 5 6 7 8 9 → 10

FAMILY LIFE / HOME RESPONSIBILITIES

The symptoms have disrupted your family life / home responsibilities:

Not at all Mildly Moderately Markedly Extremely

0 ← 1 2 3 4 5 6 7 8 9 → 10

Days Lost
On how many days in the last week did your symptoms cause you to miss school or work or leave you unable to carry out your normal daily responsibilities? _____

Days Unproductive
On how many days in the last week did you feel so impaired by your symptoms, that even though you went to school or work, your productivity was reduced? _____

Exhibit 10
Watts Connectedness Scale (WCS)

Watts Connectedness Scale (WCS)

Reference

Watts' et al.

Instructions

Reflecting on how you have felt over the past 2 weeks, please rate the following items on a scale from 'Not at all' to 'Entirely' according to how you have felt over this time period. Please answer every item, even if you are unsure or feel the item is unclear or poorly worded. Drag the indicator to a position on the scale that shows how much you agree or disagree with each of the following statements.

Response format

Each item is rated on a 0 – 100 visual analogue scale with the anchors 0 = Not at all, 100 = Entirely

Not at all  Entirely

Final items

1. *I have felt trapped in my mind.*
2. *My mind has felt connected to my heart/emotion.*
3. *I have felt connected to my senses (touch, taste, sight, smell, hearing).*
4. *I have felt connected to a range of emotions.*
5. *If I had chosen to, I could have 'sat with' painful memories.*

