6. *I have felt connected to my body.*
7. *I have been able to fully experience emotion, whether positive or negative.*
8. *I have felt alone.*
9. *I have felt connected to friends and/or family.*
10. *I have felt connected to a community.*
11. *I have felt connected to all humanity.*
12. *I have felt unwelcome amongst others.*
13. *I have felt separate from the world around me.*
14. *I have felt connected to a purpose in life.*
15. *I have felt connected to nature.*
16. *I have felt connected to a spiritual essence (in the secular or religious sense).*
17. *I have felt connected to a source of universal love.*
18. *I have seen things from a broad perspective, 'the bigger picture'.*
19. *I have felt that everything is interconnected.*

CONFIDENTIAL

Exhibit 11

Mystical Experience Questionnaire (MEQ30) – Revised

mystical experience questionnaire (meq30)

instructions: looking back on the entirety of your psychedelic session, please rate the degree to which at any time during that session you experienced the following phenomena. Answer each question according to your feelings, thoughts, and experiences at the time of the psychedelic session. In making each of your ratings, use the following scale: **0** none/not at all; **1** so slight cannot decide; **2** slight; **3** moderate; **4** strong (equivalent in degree to any other strong experience); **5** extreme (more than any other time in my life and stronger than 4). Feel free to use 'half-point in-between scores' if these are applicable.

		0	1	2	3	4	5
1	Loss of your usual sense of time. (T)						
2	Experience of amazement. (P)						
3	Sense that the experience cannot be described adequately in words. (I)						
4	Gain of insightful knowledge experienced at an intuitive level						
5	Feeling that you experienced eternity or infinity.						
6	Experience of oneness or unity with the objects and/or persons perceived in your surroundings.						
7	Loss of your usual sense of space. (T)						
8	Feelings of tenderness and gentleness. (P)						
9	Certainty of encounter with ultimate reality (in the sense of being able to 'know' and 'see' what is really real at some point during your experience).						
10	Feeling that you could not do justice to your experience by describing it in words. (I)						
11	Loss of your usual sense of where you were. (T)						
12	Feelings of peace and tranquillity. (P)						
13	Sense of being 'outside of' time, beyond past and future. (T)						

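### Section 4.4.3 plans mean change from baseline for WCS, MEQ30, CEQ and 5D-ASC, but none of the four has a pre-dose score

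*Protocol*

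**What the plan says.** Section 4.4.3 introduces its list of instruments with "Mean changes from baseline to various study visit timepoints (e.g., Study Day 7) will be calculated for the following instruments". The list has 13 entries: GAD-7, PHQ-9, NIH HEALS, BPI, C-SSRS, POMS, SDS, WCS, MEQ30, CEQ, 5D-ASC, AUDIT and DUDIT. Section 12.5 carries this into the analysis: "Analyses of changes from baseline for continuous questionnaires will be summarized descriptively by visit", with significance judged at p<0.05 for each measure and 95% confidence intervals.

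On timing, the post-dose part of Section 7.1.4 says "Nearing the 8-hour timepoint, the following clinician rating scales and participant QoL and PRO instruments should be administered", and WCS, MEQ30, CEQ and 5D-ASC are in that group.

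On recall period, the MEQ30 exhibit asks the participant to answer "looking back on the entirety of your psychedelic session", while the WCS exhibit begins "Reflecting on how you have felt over the past 2 weeks".

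For C-SSRS, Section 8.5 describes a Baseline "form that assesses lifetime suicidal ideation, intensity, and behavior" and a second form for current ideation. The form reproduced in Exhibit 7 is headed "Since Last Visit".

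**The concern.** A change from baseline needs a score taken before treatment. If an instrument is first given after the dose, the quantity named in Section 4.4.3 does not exist, whatever model the analysis plan chooses.

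The consequence differs by scale. For an instrument that rates the drug session, the error is one of classification: the data are collected at the right time and only the planned summary is wrong. For WCS the error is in data collection. Connectedness over the past two weeks is meaningful before dosing, and without that score the trial cannot describe how connectedness changed.

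C-SSRS raises a related but weaker question: whether the baseline and follow-up scores cover comparable periods.

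**Working it through.** No sample-size or power figure is at issue. The check sets the Section 4.4.3 list against the itemised visit lists and tables.

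| Instrument | Screening (7.1.3) | Day 1 pre-dose (7.1.4 or Table 2) | Pre-dose score? |
|---|---|---|---|
| GAD-7, PHQ-9, C-SSRS | yes | yes | yes |
| NIH HEALS | yes | Table 2 only | yes |
| BPI | yes | 7.1.4 only | yes |
| POMS | no | yes | yes |
| SDS, AUDIT, DUDIT | yes | no | yes |
| WCS, MEQ30, CEQ, 5D-ASC | no | no | **no** |

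Count: 3 + 1 + 1 + 1 + 3 = 9 instruments with a pre-dose score and 4 without. 4/13 = 0.31.

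Table 1 marks the four scales under Day 1, which on its own could mean before or after dosing. Table 2 settles this: each has a single mark, in the 480-minute column, in agreement with the 8-hour list in 7.1.4.

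**Could a baseline exist?**

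- MEQ30 and CEQ ask about the session as a whole. Before the session there is nothing to rate.
- 5D-ASC rates the experience against normal waking consciousness, which its instructions place at the left end of each line. The comparison is built into the item. It is given once in the trial, so no change of any kind is available.
- WCS has a two-week recall and could be completed before dosing. It is not scheduled then.

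**Day 30.** Table 1 marks WCS, MEQ30 and CEQ at Day 30; the Section 7.1.8 list for that visit contains none of them. For WCS this matters. At Day 8, one week after dosing, 14 − 7 = 7 days of the 14-day recall still fall before the dose. Day 30 is the only scheduled WCS whose recall lies wholly after dosing, and the two places disagree on whether it is collected.

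**C-SSRS.** The instrument is scheduled at Screening and again pre-dose on Day 1; in both lists the entry reads "C-SSRS (category ratings of 4 or 5 will exclude the participant". Neither place names the form. Two cases follow.

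- *Lifetime form as baseline.* As an illustration, a participant whose worst lifetime ideation was category 4, years ago, and who has none now scores 4 at baseline and 0 at follow-up: a change of −4 with no drug effect. Such a person can be eligible, since the exclusion for items 4 or 5 looks back 6 months. A participant with no lifetime ideation can only stay level or worsen. The mean is therefore biased toward improvement, but improvement is not guaranteed.
- *Interval form at Day 1 as baseline.* The forms then match, but the nominal windows do not. The window before dosing is up to about 30 days (longer if Screening is extended). The later windows are about 8 h, then 24 − 8 = 16 h, 72 − 24 = 48 h (2 days), 8 − 4 = 4 days, 30 − 8 = 22 days and 90 − 30 = 60 days.

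**The case against.** The strongest reply is that three of the four scales suffer no loss. MEQ30, CEQ and 5D-ASC are collected when they should be, nobody can compute a false change from a baseline that does not exist, and the fault is an over-inclusive list heading. That stands, and it is why these three need only a change of wording.

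It can also be said that the protocol promises baseline measures in general terms at Screening and on Day 1 (Sections 4.1 and 7.1.4), and that the analysis plan will set out formal methods. The general statements do not help, because the itemised lists that staff will follow omit these scales. An analysis plan can redefine a summary but cannot supply an uncollected score.

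For WCS, one might add that at 8 hours most of the two-week recall is still pre-dose: 14 × 24 = 336 h, of which 336 − 8 = 328 h, or 98%, precede dosing. But the answers are given after the drug experience, and the protocol does not designate that score as a baseline.

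Two stronger readings are tempting and are not supported. A reader might infer that the 8-hour WCS will be used as the baseline and so hide or reverse an effect; the document says neither, and nothing shows the direction of any distortion. A reader might also infer that C-SSRS change is biased by construction and will send a false safety message. The protocol does not say that the lifetime form is the baseline: the suicide-risk exclusion criterion separates Screening from Baseline (Visit 1), and C-SSRS is repeated pre-dose on Day 1. Section 12.3 also makes suicidal ideation and psychiatric health separate safety analyses, and Section 10.3 collects all adverse events related to psychiatric status throughout. What remains for C-SSRS is an unstated baseline and unequal windows.

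**Conclusion.** The point holds for four scales. As written, 4 of the 13 change-from-baseline summaries (31%) cannot be computed. For MEQ30, CEQ and 5D-ASC this is a misclassification. For WCS it is a gap in data collection that becomes permanent for each participant dosed, so it should be closed in the protocol. This rests only on the itemised lists in 7.1.3 and 7.1.4 and on Table 2, which agree with each other on these four scales.

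For C-SSRS the conclusion is conditional. A bias toward apparent improvement follows only if the lifetime form is the baseline. Unequal recall windows apply in either case, and the largely yes/no and ordinal items make a mean change a poor summary.

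The correction is worth making, but its reach is limited to exploratory endpoints in an open-label Phase 1 trial of up to 24 participants.

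**What to change.** 1. **WCS:** add it to the Screening list in 7.1.3 or the Day 1 pre-dose list in 7.1.4, with matching marks in Tables 1 and 2, and name that score as its baseline. The 8-hour WCS may stay; removing it is a matter of preference. For anyone already dosed, report observed WCS scores only.
2. **MEQ30, CEQ and 5D-ASC:** take them out of the change-from-baseline list in 4.4.3 and summarise them as post-session scores.
3. **Day 30:** reconcile Table 1 with Section 7.1.8 on whether WCS, MEQ30 and CEQ are collected. If MEQ30 and CEQ are repeated, label them as later ratings of the same session, not as change from baseline.
4. **C-SSRS:** state which form and which visit serve as baseline. Replace the mean change with number (%) by highest ideation category and number (%) with any behaviour, per interval, plus shift tables.

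The cost is one extra 19-item self-report form per participant at an existing visit, and edits to 4.4.3, to 7.1.3 or 7.1.4, to 7.1.8 if the reconciliation requires it, and to Tables 1 and 2. No extra visit is needed.
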